Upon return to the clinic ( $\geq 1$  week post screening visit) the RA will review the consent form with the parent or legally acceptable representative and answer any questions. The caregiver will be asked if they are still interested in continuing with participation in the study; if they agree, then the RA will complete the informed consent process and obtain their written signature on the consent form.

Once the consent form is signed and a copy has been given to the participant, the study nurse or clinician will conduct a medical examination, and a trained phlebotomist will draw blood from the child and collect a bloodspot on filter paper (see "Blood specimen collection and processing"). The RA will then proceed with the enrollment questionnaire and direct observation of the oral solution. For all children who join the study and are still breastfeeding, the enrollment questionnaire will include questions to establish a baseline breastfeeding rate (how many times a day). After direct observation of dosing with the solution, an RA will complete an IDI with the caregiver.

Training of caregivers

Caregivers will receive one 237-ml bottle of AA-ORS or placebo at enrollment along with a small cup and spoon to aid administration. The RA will train the caregiver to give the solution to their child and show them how to properly seal the bottle (containing unused solution) following solution provision (Appendix 6). The caregiver will administer the solution to their child in a private room in the clinic, under direct observation by an RA for 3 hours or until the solution has been finished, whichever comes first. Breastfeeding and solid feeding is permitted whenever desired during the 3-hour period.

Direct observation:

The goal of DOs is to directly witness the administration of AA-ORS or placebo solution and instruct caregivers to properly reseal bottles with unused solution. Target observations during the DOs include:

- Perceived palatability of study product by children.
- Perceived acceptable volume of study product by children.
- Ease of administration of study product by caregivers to their child.

Interim visits:

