The following day after enrollment, the RA will visit the caregiver in their home to review the instructions and give the caregiver six additional 237-ml bottles. The RA will instruct the caregiver to give doses using the same technique and time limit used in the clinic for the next 20 days, to reseal unconsumed solution in bottles, and store bottles in a safe location (Appendix 6). The RA will help the caregiver to select an appropriate storage location for new and used bottles of AA-ORS/placebo that is out of reach of children and protected from heat and sunlight.

Each day during follow-up, an automated text message (SMS) will be sent to remind caregivers to administer the study product, and a second message (3 hours later) will remind them to mark and reseal bottles using tape and markers provided at enrollment. If automated SMS proves unfeasible, RAs will send SMS reminders to caregivers manually. The RA will visit the home on days 2, 4, 7, and 14 to collect unconsumed solution, review instructions, provide additional bottles (on day 2 and 7), and on days 7 and 14 only weigh the children. All empty or partial bottles will be collected, and unconsumed solution will be measured as part of the longitudinal volume feasibility assessment.

Interval medical history interviews:

Caregivers will receive study nurse contact information and can contact the nurse by phone at any time during the course of the study. Periodically during dosing (days 4, 7, 14, and 21) and 1 week after the end of dosing (day 21), a study nurse will contact the caregiver by phone and check in with the caregiver to assess any potential adverse events or serious adverse events, complete the routine interval medical history/stool frequency questionnaire, ask if the child is still breastfeeding (for children who were still breastfeeding at enrollment), answer any medical questions, and provide advice, as necessary. If breastfeeding has stopped, the caregiver will be asked if the child instituted the stoppage or if the mother decided to wean. All AEs and SAEs reported by the nurse will be reviewed by the study clinician, who will provide medical advice and care as needed.

Post-dosing visit:

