**STUDY ENDPOINTS TO BE ANALYZED AND ANALYTICAL METHODOLOGY**

**Primary:** AEs and SAEs through 21 days of follow-up, and changes to dietary and digestive habits through day 14 of follow-up.

*For AEs and SAEs that occur within 21 days of enrollment, statistical comparisons will be made between the AA-ORS and the placebo solution groups using Fisher's exact test. Changes to feeding habits (normal, less frequent/less volume, more frequent/more volume), diarrhea (1–2, 3–4, 5–7, or 7+ events in 24 hours), and vomiting (none, 1, 2–5, > 6 events in 24 hours, or hospitalization) will be made using chi-square tests.*

**Primary:** Average daily product volume consumed through 14 days of follow-up, time trends in daily volume consumed, and factors that influence children's willingness and ability to ingest the product as intended.

*The average daily volume (and statistical distribution) of solution consumed by children over the 2-week period will be calculated. These descriptive data will be pooled from AA-ORS and placebo arms as the solutions are designed to taste the same. Lowess curves will be used to describe trends in volumes consumed, and linear mixed effects models will be used to test for an association between day of follow-up and product volume consumed. We will use linear regression to identify factors (e.g., child weight, length, and age) associated with a child's average daily intake.*

**Secondary:** Key factors that influence caregivers' willingness to have the product used by their children, and their perception of their children's response to its consumption.

*These qualitative analyses will use ATLAS.ti software to identify and group key themes and topics from IDI notes.*

**Exploratory:** Average plasma/serum concentrations of metabolic, gut dysfunction, systemic inflammation, and micronutrient biomarkers at baseline and day 15 of follow-up.

*Metabolic, EED, systemic inflammation, and micronutrient marker data collected at baseline will be pooled across intervention groups and used to generate descriptive statistics for the study population. The same descriptive statistics will be generated for day 15 of follow-up. Paired student's t test will be used to compare these continuous parameters between baseline and day 15 of follow-up.*

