#### DO of product administration:

DO will be conducted with caregivers and their child during the very first study product administration at the enrollment visit. AA-ORS or placebo solution will be provided to participants by study staff. The DO will last up to three hours, depending on how quickly the child drinks the product. The researcher will take notes contemporaneously during the DO.

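### The planned test of daily volume against day of follow-up does not separate the single clinic-observed first dose from the later home doses, so a day-1 difference alone could appear as a time trend

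*Combined protocol and SAP*

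**What the plan says.** In section C.xi (study endpoints and analytical methodology), the second primary endpoint is "Average daily product volume consumed through 14 days of follow-up, time trends in daily volume consumed", together with factors that affect intake. The trend is to be tested formally as follows: "linear mixed effects models will be used to test for an association between day of follow-up and product volume consumed". The form of the day term is not stated. A smoothed plot is planned as well, but for description only: "Lowess curves will be used to describe trends in volumes consumed". Nothing in the analysis section adds a clinic/home or first-dose term, leaves out day 1, or plans a sensitivity analysis for the trend.

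Section C.iii shows that the first dose differs from the rest:

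- **Setting.** Under Training of caregivers, the first dose is given "in a private room in the clinic, under direct observation by an RA for 3 hours or until the solution has been finished". Section D.iii confirms that this applies once: "DO will be conducted with caregivers and their child during the very first study product administration at the enrollment visit". Table 4 marks direct observation of feeding at enrollment only.
- **Circumstances.** It is the child's first taste of the product and the caregiver's training session. It follows a medical examination and a blood draw, after which "The RA will then proceed with the enrollment questionnaire and direct observation of the oral solution".
- **Measurement.** Key Activities (item 4) has the day-1 leftover measured and recorded at the end of the observed period and then thrown away. For home doses, the caregiver reseals the bottle and staff collect it at visits on days 2, 4, 7 and 14: "All empty or partial bottles will be collected, and unconsumed solution will be measured as part of the longitudinal volume feasibility assessment".

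**The concern.** Setting, observation, novelty and method of measurement all change once, between day 1 and day 2, at the edge of the day range. A model with day as its only time variable cannot tell such a step from a gradual change. If children drink more on day 1 because staff are coaching and watching, the fitted slope is pulled down. If they drink less because of the strange room, the new taste or the blood draw, it is pulled up. Product spilled or shared at home would count as consumed and would also widen the gap.

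At stake is a statement that children's intake falls, or rises, over two weeks of use. The aims section lists trends in the dose consumed among the things the pilot should determine, and its results are to inform the design of an efficacy trial.

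**Working it through.** **The plan's own figure.** The documents give no figure for the volume trend. The sample size rests on safety: 30 per arm and a true AE rate of 10% give 1 − 0.9^30 = 95.8% for at least one AE, as in Table 6. It reproduces, but says nothing about the trend.

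**Inputs.**

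- Days 1–14, from the endpoint definition. The Interim visits text instructs dosing for a further 20 days, and Safety Monitoring numbers bottles up to 21. Those passages must be reconciled with the 14-day regimen, and the model should state its day range.
- About 60 children: 66 enrolled, dropout of at most 10%, 66 × 0.9 = 59.4.
- Assumed, because the documents do not give them: day-1 shift D of 10, 25 or 50 ml; day-to-day SD σ of 40 to 80 ml; between-child slope SD τ of 2 ml/day; two-sided 5% test (P < 0.05 is stated only with the biomarker comparisons); no true trend over home dosing.

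**Slope from day 1 alone.** This step needs no assumed SD, only a straight-line day term.

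- Mean day = 7.5; Sxx = Σ(day − 7.5)² = 227.5.
- Slope = (1 − 7.5) × D / 227.5 = −D/35 ml/day.
- Day 1 supplies 6.5² / 227.5 = 18.6% of Sxx, against 1/14 = 7.1% if days counted equally. Day 14 supplies the same share, so the two tie for highest leverage.
- D = 25 ml gives −0.71 ml/day, or −9.3 ml across the 13-day span. D = 50 ml gives −1.43 ml/day, or −18.6 ml.

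**Chance of a significant trend with no true home trend.** SE = √(σ²/(60 × 227.5) + τ²/60).

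- σ = 40: √(0.1172 + 0.0667) = 0.429.
- σ = 80: √(0.4689 + 0.0667) = 0.732.
- Rejection probability = Φ(|D|/35/SE − 1.96) + Φ(−|D|/35/SE − 1.96).

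| D (ml) | slope size (ml/day) | σ = 40 | σ = 80 |
|---|---|---|---|
| 10 | 0.29 | 10% | 7% |
| 25 | 0.71 | 38% | 16% |
| 50 | 1.43 | 91% | 50% |

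**Check by simulation.** Volumes were bounded at 0–237 ml, with 60 children and 4,000 runs per scenario. For shifts of 20, 40 and 60 ml in either direction, and σ from 40 to 80 ml, a significant trend appeared in about 11–25%, 30–74% and 56–97% of runs. With days 2–14 only, the rate was 4.2–6.1% at every shift tried.

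**Effect on the mean.** The 14-day average moves by D/14: 25/14 = 1.8 ml; 50/14 = 3.6 ml.

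**Cost in precision.** For days 2–14, Sxx = 182. With no between-child slope variation the SE ratio is √(227.5/182) = 1.118. With τ = 2 ml/day it is 1.08 at σ = 40 and 1.10 at σ = 80.

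**The case against.** **The form of the day term is not given.** The plan names a class of model, not a straight line. This stands as a condition. A linear term is the natural reading; with day as a factor, the overall test would still respond to a day-1 difference, although the day-1 estimate would show where it lies.

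**A first-dose difference may be a real part of the time course.** Getting used to a new taste is a genuine effect, and palatability is something the observed dose is meant to assess. With one clinic dose per child, setting and first exposure are completely confounded, and no indicator can separate them. This stands, and it argues against simply discarding day 1. It does not rescue the single slope, which would describe a one-off step as a steady change.

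**The plan has partial safeguards.** Caregivers are to use the clinic technique and time limit at home, they get twice-daily text reminders, and a Lowess curve will be drawn. These may narrow the gap or make it visible. None changes the test, and dropping day 1 after seeing the curve would be post hoc.

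**The consequence is limited.** The risk table ties dosing guidance to the average volume, which day 1 hardly moves. No decision rule rests on the slope's P value, and the limitations section promises restrained conclusions. This stands and sets the weight of the point.

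**What a reader might infer too far.** A reader might conclude that the trial will report a false trend, or that its dosing or safety results are compromised. The documents do not support that: they give no clinic–home difference, not even its direction, and the high probabilities need a shift of 50 ml, about 21% of the 237 ml bottle (50/237).

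**Conclusion.** The point holds as a possibility that the plan leaves open. As written, the trend test does not distinguish the one observed clinic dose from the home doses. If day enters linearly, a day-1 difference of D ml by itself yields a slope of −D/35 ml/day. Whether that matters depends on D and the variability of intake, both unknown: under the stated assumptions the chance of a significant trend runs from near nominal (7–10% at 10 ml) to 50–91% at 50 ml.

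It concerns the interpretation of the trend only. The average daily volume shifts by D/14, and the safety comparison between arms is not touched, because both arms take the first dose in the same setting. It is a cheap improvement to the analysis plan, not a flaw in the design.

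**What to change.** In section C.xi, under the second primary endpoint:

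- State the day range and the form of the day term.
- Prespecify that the mixed-model trend is reported twice: over days 1–14, and either with a day-1 (clinic, first-dose) indicator or on days 2–14.
- Show day 1 separately on the Lowess plot.
- State that a trend over home dosing will be claimed only if it holds without day 1.

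The cost is one model term or one refit on data already being collected. The standard error of the slope rises by at most about 12%. The indicator also absorbs any genuine first-exposure effect along with the clinic effect, and omitting day 1 drops the only observed dose. That is why both results should be reported.

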#### Objectives

**PRIMARY OBJECTIVE:** To determine the safety of AA-ORS among children with mild to moderate stunting, administered as a daily dose over 2 weeks, ad libitum up to 237 ml in 3 hours.

*Safety assessment in children will compare adverse event (AE) and serious adverse event (SAE) rates and changes to dietary and digestive habits between children receiving AA-ORS versus an inactive placebo solution containing no amino acids.*

**PRIMARY OBJECTIVE:** To determine the feasibility and well-tolerated dose of AA-ORS among children with mild to moderate growth stunting administered as a daily dose over 2 weeks, ad libitum up to 237 ml in 3 hours.

*User preferences among children include average daily volume consumed over 14 days, trends in volume consumed, and factors that influence children's willingness and ability to ingest the product as intended.*

**SECONDARY OBJECTIVE:** To determine the perceptions among caregivers on the use and acceptability of this product as a potential intervention for EED.

*Acceptability by caregivers includes factors that influence their willingness to have the product used by their children and their perception of their child's response to its consumption.*

**EXPLORATORY OBJECTIVE:** To determine the impact of AA-ORS on gut dysfunction, metabolism, gut and systemic inflammation, and micronutrient status.

*Impact of AA-ORS on gut dysfunction, systemic inflammation, and micronutrient status will be assessed by comparing non-invasive biomarker levels in blood samples collected following the intervention. These biomarkers will be assessed in both groups at baseline in order to have setting-specific descriptive data with which to power a future EED efficacy trial.*

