#### vii. Exclusion criteria for each group

##### *Exclusion Criteria*

##### Pediatric and caregiver pairs (must meet none of the exclusion criteria for either category):

###### Child:

1. Has any sign of acute illness, including but not limited to fever, cough, and diarrhea.
2. Is wasted (weight for length z-score  $< -2$  or mid-upper arm circumference [MUAC]  $< 12.4$  cm) or has pitting edema.
3. Is exclusively breastfed.

4. Is seeking medical attention at the health facility other than for routine, preventative care (e.g., immunization visit, vitamin supplementation).
5. Has suffered within the prior week from illnesses that might impact nutritional status (e.g., severe diarrhea or pneumonia; vomiting; persistent diarrhea; cleft lip or palate; blindness; tuberculosis; jaundice; renal or cardiac disease; cerebral palsy; known metabolic disorders; and chromosomal disorders, including trisomy 21).
6. Medical history of chronic health condition (i.e., HIV, hepatitis B or C, end stage renal disease, severe liver disease—absence of a diagnosis is sufficient).
7. Participating in any other clinical trials.
8. Recent (prior 2 weeks) use of antibiotics or any other medical treatments (including ORT, but not including vaccines or vitamin/mineral supplementation).
9. Cannot give the necessary biological (blood) sample.

Caregiver:

Reports diarrhea in the household in the prior 7 days.

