*Unpaired student's t test will be used to compare these continuous parameters between the two study groups at day 22. A difference with  $P < 0.05$  will be considered statistically significant. However, there is limited statistical power to make such comparisons between study groups for biomarker outcomes.*

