### i. Risks to research study participants/groups

#### *Risk Considerations*

The proposed study is expected to be of minimal risk as the study AA-ORS is a medical food product regulated by the US FDA. As a result, we do not anticipate any adverse events for this study related to the administration of AA-ORS, but we will include a control arm in order to better assess the safety of this product in children with mild-moderate stunting. Children with mild to moderate stunting are at increased risk for morbidity and mortality, so we anticipate that participants may report diarrhea or respiratory infections at high rates, regardless of receipt of active AA-ORS or placebo. While there is mounting evidence that microbiome immaturity contributes to growth deficits in LRS, any changes to the microbiome composition and diversity from provision of AA-ORS are likely to be transient, based upon previous observations among infants and children provided probiotic-supplemented formula or ready-to-use supplementary food (43, 44).

This study involves blood specimen collection. The collection of these samples involves venipuncture, which may cause discomfort, pain, introduction of infection, bleeding, fainting, or bruising. Precautions will be taken to avoid introduction of infection by disinfecting the site of venipuncture and using sterile equipment. The risk of bleeding and bruising will be minimized by immediate application of pressure after venipuncture. The child will be restrained appropriately by the caregiver to prevent kicking of the phlebotomist. A thorough description of potential risk considerations and mitigation strategies is outlined in Table 7.

**Table 7.** Known risks and mitigation strategies for SAFE study participants.

Potential risk to participant	Concern	Study design feature intended to minimize risk	Rationale for the necessity of exposing participants to risk

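### The between-arm biomarker test leaves out the measured baseline, and the baseline-to-day-15 paired test has no control and cannot show an impact of AA-ORS

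*Combined protocol and SAP*

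**What the plan says.** The exploratory objective (C.ii, Objectives) is "To determine the impact of AA-ORS on gut dysfunction, metabolism, gut and systemic inflammation, and micronutrient status". The same section says that impact "will be assessed by comparing non-invasive biomarker levels in blood samples collected following the intervention", and gives the baseline samples a planning role: "These biomarkers will be assessed in both groups at baseline in order to have setting-specific descriptive data".

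The analysis text is in C.xi, Study endpoints to be analyzed and analytical methodology. Baseline marker data "will be pooled across intervention groups and used to generate descriptive statistics for the study population", and the same summaries are to be produced for day 15. Then a paired "t test will be used to compare these continuous parameters between baseline and day 15 of follow-up". No arm is named for that test. The next sentence says that an unpaired t test "will be used to compare these continuous parameters between the two study groups", and places this comparison at day 22. No baseline term is mentioned. A P<0.05 threshold follows, with a remark that power for comparing the groups is limited.

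Table 4 and Blood Specimen Collection and Processing (C.iii) provide for two blood draws per child, at enrollment and at the day-15 visit. No draw is scheduled for day 22.

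At entry, a child is excluded who "Has any sign of acute illness, including but not limited to fever, cough, and diarrhea" (C.vii). Antibiotics in the prior 2 weeks and household diarrhea in the prior 7 days also exclude. For the follow-up period, Risk Considerations (D.i) states: "we anticipate that participants may report diarrhea or respiratory infections at high rates, regardless of receipt of active AA-ORS or placebo".

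**The concern.** Two features of the plan fit poorly with an objective about the impact of the product.

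First, the only randomised biomarker comparison ignores information that the trial has already paid for. Each child's own baseline value usually predicts the follow-up value. Leaving it out widens the interval and leaves any chance imbalance between two arms of about 30 uncorrected. The plan itself says that power here is limited.

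Second, the only test that uses baseline has no control. If it is run on all children together, half of them received placebo. Children are selected to be free of acute illness at the first draw, no such condition is stated for the second, and illness is expected in both arms in between. A shift in CRP, AGP or other markers with no product effect is therefore plausible. The plan attaches a significance test to this change without saying what it is for.

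At stake is what carries forward. The plan intends these data to inform the design and sample size of later EED trials. A change credited to the wrong cause, or a variance larger than a better analysis would give, would feed into that planning.

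**Working it through.** **Inputs from Sampling Strategy (C.iii).** sCD14 SD 520 ng/ml; placebo mean 1,715 ng/ml; difference 376 ng/ml; 30 per arm after dropout from 33 (33 × 0.9 = 29.7). Alpha is 0.05, taken as two-sided. The correlation r between baseline and follow-up and the size of any drift are not in the documents. Both are assumed and shown as ranges. The SD is taken as equal at the two time points.

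**Step 1: the plan's own figure.** 376 / 1,715 = 21.9%, as stated. SE of the between-arm difference = 520 × √(2/30) = 134.3 ng/ml, and 376 / 134.3 = 2.80. Power is 80.0% by the normal approximation and 78.6% by the noncentral t with 58 df. The stated value of about 80% is reproduced and is not in dispute.

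**Step 2: baseline adjustment.** ANCOVA replaces the SD by a residual SD of 520 × √(1 − r²), with 57 df. By the t calculation, the standardised difference detectable with 80% power at 30 per arm is 0.736, and 0.736 × 520 = 383 ng/ml. The same multiplier is applied to each residual SD.

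| Assumed r | Residual SD (ng/ml) | Power for 376 ng/ml | Detectable at 80% power (ng/ml) |
|---|---|---|---|
| unadjusted | 520 | 79% | 383 |
| 0.3 | 496 | 82% | 365 |
| 0.5 | 450 | 89% | 331 |
| 0.7 | 371 | 97% | 273 |

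**Step 3: chance imbalance.** The SE of the baseline difference between arms is also 134 ng/ml. An imbalance of one SE shifts the unadjusted follow-up contrast by about r × 134, that is 40, 67 or 94 ng/ml at r = 0.3, 0.5 or 0.7. ANCOVA removes this shift.

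**Step 4: does drift reach the between-arm test?** In a simulation of 20,000 trials (30 per arm, r = 0.5, no product effect, equal drift in both arms), the unadjusted between-arm test gave P<0.05 in 5.1%, 4.9% and 4.9% of trials at drift 0, 0.3 and 0.5 SD. Common drift cancels.

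**Step 5: what the pooled paired test estimates.** With drift δ in both arms and product effect D, the mean change over 60 children is (30 × (δ + D) + 30 × δ) / 60 = δ + D/2. The two parts cannot be separated.

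**Step 6: how often drift alone is significant.** SD of change = SD × √(2(1 − r)), which is 1.18, 1.00 or 0.77 SD at r = 0.3, 0.5 or 0.7. The noncentrality is (drift/SD of change) × √60. For 0.3 SD it is 2.324/1.183 = 1.96, 2.324/1.00 = 2.32, or 2.324/0.775 = 3.00. Share of trials with P<0.05 and no product effect:

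| Assumed drift | On the sCD14 scale | r = 0.3 | r = 0.5 | r = 0.7 |
|---|---|---|---|---|
| 0.2 SD | 104 ng/ml | 25% | 33% | 50% |
| 0.3 SD | 156 ng/ml | 49% | 63% | 84% |
| 0.5 SD | 260 ng/ml | 90% | 97% | over 99% |

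The simulation in step 4 gave 63% for the paired test at 0.3 SD and r = 0.5, in agreement. Running the paired test within each arm would separate the arms but would not remove the drift. The Benjamini-Hochberg step (C.xi, Issues with missing data and multiplicity) does not help either: a change caused by drift is a real change, and only its attribution to the product would be wrong.

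**The case against.** The strongest reply is that the plan does not test impact with the paired comparison. The Objectives section ties impact to samples taken after the intervention and gives baseline a descriptive role. Study Approach and Study Population (C.iii) likewise frames the question as a difference between AA-ORS and placebo at the end of follow-up. That stands. A reader might infer that the plan will present a pooled before-after change as a product effect. No section says so, although none rules it out.

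A reader might also infer that, because the between-arm test ignores baseline, it too lets drift pass for an effect. It does not: randomisation makes the unadjusted follow-up comparison valid, as step 4 shows.

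Three further points stand in part. Pooling of the paired test is an inference. The text states pooling for the baseline summaries, and the paired-test sentence names no arm; the two study groups appear only in the next sentence, so pooling is the natural reading but not a stated fact. The case for drift is qualitative: the documents give neither an illness rate nor a marker response. And the plan openly concedes low power and an exploratory purpose, and promises in C.xii not to conclude beyond its methods. Those concessions concern power. None mentions drift or baseline adjustment, and neither change below needs a larger trial.

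**Conclusion.** The point holds as two limited statements.

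The between-arm test is valid but inefficient. With the plan's sCD14 inputs, adjustment for baseline raises power for 376 ng/ml from about 79% to 82%, 89% or 97%, and lowers the detectable difference from 383 to 365, 331 or 273 ng/ml, at r = 0.3, 0.5 or 0.7. The gain is small if r is near 0.3 and substantial near 0.7; the documents do not say which applies, and other markers may differ from sCD14.

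The paired test, on its natural pooled reading, has no control and cannot show an impact of AA-ORS. The rates in step 6 illustrate what drift of a given size would do. They do not estimate the drift in this trial.

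The documents do not support the stronger reading that the planned analysis of impact is biased by drift. There is also a plain inconsistency to settle: the between-arm comparison is placed at day 22, when no blood is drawn.

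**What to change.** In C.xi, exploratory endpoint:

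- Make the between-arm comparison an ANCOVA of the post-dosing value on arm and the child's own baseline value, on the log scale for skewed markers, with the estimate and 95% CI. Base any statement on impact on this analysis alone.
- Label the baseline-to-day-15 comparison as descriptive, and show baseline, day 15 and change by arm. Keep the pooled baseline summary for planning later trials.
- Reconcile day 22 with the day-15 draw in Table 4 and in Blood Specimen Collection and Processing.

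Do not try to deal with drift by excluding children who are ill at the second draw. Illness after randomisation may itself be affected by the product (Study Approach and Study Population treats diarrhea frequency as a possible difference between the arms), so the exclusion could bias the randomised contrast.

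The cost is a few sentences in the analysis plan and one degree of freedom per model (58 to 57 with 30 per arm). No new visits, samples or assays are needed.
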